To calculate the necessary sample size, the following parameters were considered: a prevalence of mental disorders of 27.8% and an identification rate of 30% of these cases (9 cases per 100 children, per year). This indicator (which corresponds to scenario 2 and specific objective 4) was taken as one of the most important achievements and reflects the impact of the intervention as a whole. To accept the fulfillment of our hypothesis, it will be necessary to double the identification rate to 60% of cases (18 cases per 100 children, per year). In this way, it is a comparison of proportions, where:  $p_1 = 0.3$ ,  $p_2 = 0.6$ , a confidence level of 95% for a unilateral test and a power level of 90%, 56 children are needed in each group. However, it is expected to work with a much larger sample: if it is considered that in each establishment there are 30 children per grade and only one course per level (from 1st to 8th grade). This would lead us to a potential sample of 240 children per establishment, which implies 480 in intervention facilities and 480 in control facilities.

Development of fieldwork. The development of the fieldwork has three fundamental stages: 1) Implementation of the ECO-Neighborhood Network strategy in the 1 selected neighborhood, (months 1

to 18), 2) the participatory construction of the components of the intervention (months 12 months); and 3) pilot-level evaluation of this intervention (months 12-24).

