3. The third part (months 12 to 24) consists of carrying out a pilot test taking 4 educational establishments located in two different territories of the commune of Valparaíso, in which the intervention will be carried out, and its results will be compared with 4 other equivalent educational establishments, from those same territories, which serve as control. Pre- and post-intervention assessments will be carried out, using a children's mental health knowledge survey, while referrals from facilities to the corresponding CESFAM will be recorded. Results will be compared between intervention and control results. Information is also collected to assess the participation of teachers in the intervention (feasibility analysis).

At the end of the intervention in the establishments that were the object of it, the quantitative indicators and results that were collected will be synthesized, and a qualitative analysis will be carried out (DEXPLIS design), based on discussion groups that involve the interested parties (teachers, mental health professionals and managers of both sectors). in which the results and achievements will be analyzed, barriers and facilitators of the process will be established, all of which will allow to complete the evaluation in a participatory way and to improve the components of the intervention, based on the empirical experience carried out.

After the end of the intervention, the intervention will also be carried out in its two components (teachers and health-education network) in the 4 establishments that served as control. In this way, an ethical requirement of not depriving the rest of the participants of a beneficial intervention is met. (Months 18 to 24)

Indicators, instruments and analysis procedures. For the detailed description of this point, the effectiveness analysis and the feasibility analysis of the pilot intervention are separated.

1) Evaluation of the effectiveness of the intervention. The effectiveness evaluation is based on comparing the following indicators between intervention and control establishments.

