- a) Level of knowledge of the teachers, using an *ad hoc* questionnaire, which is built in the phase prior to the intervention and validated by this team (which incorporates teachers). The conceptual framework of literacy in child and adolescent mental health will be used. This questionnaire will include all the aspects that are part of the training program aimed at teachers and will allow them to obtain scores for their different modules or dimensions. A test and semantic adaptation will be carried out with teachers from establishments in other sectors of the commune, which do not participate in the project, prior to its use within the project. It is expected that in the initial assessment (baseline), the results will be similar in the teachers of the intervention and control establishments. At the end of the intervention it is expected that scores have improved significantly in intervention facilities and have not changed in control facilities.
- b) Rates of referral of mental health problems in children. In each project establishment (intervention and control) a centralized register will be kept of the children indicated by their teachers who require mental health care during the intervention. This will also allow for centralized coordination for referral to the relevant CESFAM. In this way the detection rate can be calculated.
- c) Waiting time between referral from the educational establishment to professional care at the corresponding CESFAM. This indicator is obtained from the centralized register in each educational establishment, which includes the date on which it coordinated with CESFAM for its attention, and the registration of the first attention in the latter. The time elapsed between the two is the waiting time that will be used as an indicator.
- d) Rate of accuracy for referral of children with suspected psychiatric disorders from the school to health care. Each “case” referral will apply the Strength and Difficulties Questionnaire (SDQ). 25 items (scale 0-2).

2) Evaluation of the feasibility of the intervention. Feasibility assessment uses a combination of quantitative (indicator) and qualitative methods, which are described below.

- a) Level of interest of teachers in the intervention: It is estimated through the percentage of teachers who agree to start the training course, out of the total number of teachers who were invited (which would be the totality of each educational establishment).

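### Success is defined as detecting 60% of true cases, but the planned register counts every teacher-indicated child and the number of true cases per school is never measured

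*Combined protocol and SAP*

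**What the plan says.** The sample size paragraph of section 3.1 starts from "a prevalence of mental disorders of 27.8% and an identification rate of 30% of these cases (9 cases per 100 children, per year"). It names this indicator, tied to specific objective 4, as one of the most important achievements. For success, "it will be necessary to double the identification rate to 60% of cases (18 cases per 100 children, per year"). With p1 = 0.3, p2 = 0.6, 95% confidence for a one-sided test and 90% power, it concludes that "56 children are needed in each group". It then describes the expected sample as much larger: 240 pupils per school, "which implies 480 in intervention facilities and 480 in control facilities".

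The measurement comes later in the same section. Under indicator 1b, "a centralized register will be kept of the children indicated by their teachers who require mental health care during the intervention", and "In this way the detection rate can be calculated". No denominator is given. Indicator 1d is a separate accuracy rate for referrals: the SDQ (25 items, each scored 0-2) is applied to each referred case. No cut-off or informant is named, and nothing says that an SDQ result keeps a child in the 1b count or removes one. On the comparison, "The effectiveness evaluation is based on comparing the following indicators between intervention and control establishments", so 1b and 1d are both compared between arms. Hypothesis 3 and specific objective 5 set a separate mark of more than 80% for the relevance of referrals.

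**The concern.** The success criterion and the planned count measure different things. The criterion has true cases as its denominator and detected true cases as its numerator. The register supplies children whom a teacher judged to need care. That judgement is not confirmed before the detection rate is calculated, and no procedure screens all pupils, so the denominator is not observed in any school.

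This matters more than usual here because the intervention trains the people who generate the count. Training may change how many children teachers indicate, how accurately they do so, or both, and a raw referral rate cannot separate the two. The outcome affected is the one used to size the study, and the results are meant to inform the design of a larger trial.

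**Working it through.** **Inputs.** From section 3.1: prevalence 27.8%; identification 30% and 60% of cases, given as 9 and 18 per 100; 90% power; one-sided 5%; 56 per group; 480 pupils per arm. From hypothesis 3 and objective 5: the 80% relevance mark. The documents give no false-referral rate, so relevance values are assumptions.

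**1. The stated 56.** Pooled-variance formula without continuity correction:

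n = [z_α √(2p̄(1−p̄)) + z_β √(p1(1−p1) + p2(1−p2))]² / (p2−p1)²

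With p1 = 0.3, p2 = 0.6, p̄ = 0.45 and z_β = 1.2816:
- Two-sided 5% (z_α = 1.960): (1.960 × 0.7036 + 1.2816 × 0.6708)² / 0.09 = 55.7, so 56.
- One-sided 5% (z_α = 1.645): (1.645 × 0.7036 + 1.2816 × 0.6708)² / 0.09 = 45.2, so 46.

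The figure of 56 is right for a two-sided test but does not match the one-sided label.

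**2. The unit of 56.** The proportions 0.3 and 0.6 are shares of true cases, so 56 counts true cases. At 27.8% prevalence that is 56 / 0.278 = about 202 pupils per arm.

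**3. The per-100 marks.** 0.278 × 0.30 = 8.34 per 100 and 0.278 × 0.60 = 16.68 per 100, against the stated 9 and 18.

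**4. The absolute mark.** Share of cases detected = (indicated per 100 × relevance) / 27.8. With 18 indicated and 80% relevance: 18 × 0.80 = 14.4 true cases, and 14.4 / 27.8 = 51.8%. The count of 18 would be met while the 60% criterion is missed. Reaching 60% at that relevance takes 16.68 / 0.80 = 20.9 indicated per 100.

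**5. The between-arm ratio.** True-case ratio = raw ratio × (relevance in intervention schools / relevance in control schools). For a raw ratio of 2.0:
- equal relevance in both arms: 2.0, with no distortion;
- 80% in intervention schools, 100% in control schools: 2.0 × 0.8 / 1.0 = 1.6;
- 100% in intervention schools, 80% in control schools: 2.0 × 1.0 / 0.8 = 2.5.

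**6. Sample size per enrolled pupil.** The same formula with 0.0834 v 0.1668 gives 268 per arm one-sided or 329 two-sided, at 90% power and before any allowance for clustering by school. The expected 480 exceeds both.

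**The case against.** The strongest reply is that accuracy is already an indicator. It is compared between arms, and the 80% objective would expose gross over-referral. If relevance is the same in both arms, the raw ratio equals the true-case ratio exactly. This stands, and it narrows the point: the ratio is distorted only if relevance differs between arms. What remains is that nothing ties the accuracy result to the detection conclusion, so detection could be declared successful whatever accuracy shows. Equal relevance also does not rescue the absolute mark (step 4).

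It can also be said that 9 and 18 are rounding, since the ratio is 2.0 either way and 56 does not depend on them. That is fair for the sample size. It is not fair for the success mark, because 18 per 100 would be 18 / 27.8 = 64.7% of cases even if every referral were correct.

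Three stronger readings are tempting, and the documents do not support them.
- **That raw counts overstate the benefit.** The direction is unknown. More false positives would overstate it, and better accuracy after training would understate it.
- **That 56 against 268 or 329 shows an underpowered study.** Those figures are in different units. The like-for-like figure for 56 is about 202 pupils, and 480 per arm exceeds all of them before clustering. Elsewhere section 3.1 has four intervention schools, and "its results will be compared with 4 other equivalent educational establishments", which at 240 pupils each would be 960 per arm.
- **That the plan contradicts itself on how the 80% objective is measured.** The visible work plan row refers to entry into treatment and indicator 1d to the SDQ, but the table breaks off inside objective 5 in the available text. Nothing can be concluded from that.

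**Conclusion.** The concern holds in a limited form. As planned, the data give teacher-indicated children per school. They cannot show whether 60% of cases were identified, because true cases are not measured and the count is not linked to the SDQ.

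The effect on the between-arm ratio depends on a difference in referral relevance that the documents do not quantify. The range of 1.6 to 2.5 around a raw ratio of 2.0 is an illustration. Each end assumes 80% relevance in one arm and 100% in the other, and the 80% is the study's own target, not an observed value. The 51.8% figure likewise assumes 80% relevance, together with the stated prevalence.

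Three planning statements need correcting whatever relevance turns out to be: the marks of 9 and 18, the unit of 56, and the one-sided label. None of this shows a loss of power. The point should be fixed before analysis; it does not undermine the trial.

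**What to change.** **Change.**
- In both arms, report SDQ-positive referrals per 100 enrolled pupils beside the raw referral rate, using the SDQ already planned for each referral. Fix the cut-off in advance and name one informant, the same in both arms.
- Read the objective 4 comparison from the two rates together. Call the new rate screen-positive referral, and do not describe the raw rate as a percentage of cases.
- If the informant is the trained teacher, state that training may shift the SDQ ratings themselves. The fix does not remove that problem.
- Restate the marks as 8.3 and 16.7 per 100, state that 56 refers to true cases, and make the one-sided or two-sided label agree with the calculation.

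**Cost.** Analysis-plan wording, a cut-off and a named informant; no new instrument. The outcome inherits SDQ misclassification. If some referrals are SDQ-negative, there are fewer events and the interval is slightly wider. As an illustration, assume 80% relevance in both arms, an SDQ that classifies perfectly, and 480 pupils per arm. The raw rates would be 8.34 / 0.8 = 10.4 and 16.68 / 0.8 = 20.9 per 100. With SE(log ratio) = √[(1−a)/(na) + (1−b)/(nb)], a raw ratio of 2.0 has SE 0.161 and 95% CI 1.46 to 2.74. The screen-positive ratio, from 8.34 and 16.68 per 100, has SE 0.182 and 95% CI 1.40 to 2.86. Both ignore clustering, so the real intervals will be wider.

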### **3. METHODOLOGY, ETHICS AND PLANNING**

#### **3.1. METHODOLOGY AND PROCEDURES**

Research design. This project corresponds to an evaluation of the preliminary effectiveness and feasibility of a multi-component pilot intervention. The program will be evaluated through a cluster randomized controlled trial (RCT)

The project activities are organized around two clearly defined stages: one of participatory construction, and another of evaluation of the effectiveness and feasibility of the pilot intervention. They are explained in detail below.

Effectiveness is studied through a mixed design (subtype DEXPLIS, explanatory design sequence), which begins with a quantitative study of quasi-experimental type (comparing equivalent intervention and control facilities) and is followed by a qualitative study to analyze the implementation process and results of the pilot to intervention(including its barriers and facilitators).

The reliability is studied through indicators of participation of teachers in the intervention (initial interest and retention over time), by the satisfaction of teachers and those who participate in the articulation of local health-education networks, and with the analysis of barriers and facilitators at all levels.

Universe and sample. The universe to which the results of this study could be extended are public educational establishments. For this study, two neighborhoods of the commune of Valparaíso were selected. Therefore, the selection of the territories is not random, but the selection of the 2 establishments in each territory is. The inclusion criteria are that they are public schools and have 1st to 8th levels of primary education. The list of establishments that exist in that sector and that meet the inclusion criteria will be taken and will be selected using some random method, 2 schools of each neighborhood (4 in total) will be initially assigned to the intervention and 2 will serve as a control (four in total). As previously described, in a second moment the intervention will be carried out in the establishments that served as control for ethical reasons.

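### The 90% power from 56 children per group does not follow from the stated test or from assigning whole schools, so power for the detection outcome is not established

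*Combined protocol and SAP*

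**What the plan says.** All of this is in section 3.1 unless another section is named.

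- **Design.** "The program will be evaluated through a cluster randomized controlled trial (RCT"). A later paragraph of the section also calls the quantitative part quasi-experimental.
- **Allocation.** Under Universe and sample, two schools per neighbourhood go to each arm: ("4 in total) will be initially assigned to the intervention and 2 will serve as a control (four in total"). The description of the third stage agrees, with "4 other equivalent educational establishments, from those same territories, which serve as control".
- **Effect assumed.** "a prevalence of mental disorders of 27.8% and an identification rate of 30% of these cases (9 cases per 100 children, per year"), against a target to "double the identification rate to 60% of cases (18 cases per 100 children, per year").
- **Sample size.** With p1 = 0.3 and p2 = 0.6, "a confidence level of 95% for a unilateral test and a power level of 90%, 56 children are needed in each group". The plan then expects many more children: 240 per school, "which implies 480 in intervention facilities and 480 in control facilities".
- **Outcome source.** Effectiveness indicator b) is a register in each school of the children whom teachers flag as needing care. No case-finding among unflagged pupils is described.
- **Crossover.** After the intervention period "the intervention will also be carried out in its two components (teachers and health-education network) in the 4 establishments that served as control", dated months 18 to 24.
- **Work plan (section 3.3).** Under objective 4, two comparison schools are drawn from a neighbourhood without the intervention.
- **Claim.** Hypothesis 2 (section 2.3) and specific objective 4 (section 2.4.2) look for a significant improvement in the detection rate.

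**The concern.** Pupils in one school share teachers, a register and a referral route, so their outcomes are correlated. With whole schools assigned, the precision of the comparison depends on the number of schools and on how much detection varies between them. Adding pupils in the same schools does not reduce that variation. A sample size for independent children therefore cannot support a power statement for this design.

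The calculation also disagrees with the rest of the plan: the number does not match the stated one-sided test, the denominator is not the one used for the pupil count, and the pupil count does not match the number of schools.

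Detection is the outcome chosen to size the study, and a significance claim is planned on it. If the result is null, a reader who trusts the 90% will take it as evidence against a doubling of detection. The Summary says the results will inform the design of a larger study, which could inherit the same calculation.

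**Working it through.** **1. Reproducing the 56.** Inputs from section 3.1: p1 = 0.3, p2 = 0.6, 90% power, equal groups. Standard pooled-variance formula, with p̄ = 0.45:

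n = [z_α √(2p̄(1−p̄)) + z_β √(p1(1−p1) + p2(1−p2))]² / (p2−p1)²

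- One-sided 5%, as stated: 45.2, so 46 per group.
- Two-sided 5%: 55.7, so 56 per group, an exact match. A one-sided 2.5% test gives the same number.
- With 56 per group and independent children, power is 94.8% on the stated one-sided test and 90.2% two-sided.

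**2. Denominator.** The 0.3 and 0.6 are shares of children with a disorder. At 27.8% prevalence, 56 such children correspond to 56 / 0.278 = 201 pupils. The plan sets 56 beside a count of all pupils. A register of flagged children gives no count of children with a disorder who were missed, so the share detected cannot be calculated from it.

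**3. Rates per 100 pupils.** 0.278 × 0.30 = 8.34 and 0.278 × 0.60 = 16.68, against the stated 9 and 18. This is minor and does not enter the 56.

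**4. Pupils per arm.** 480 / 240 = 2 schools; 4 × 240 = 960.

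**5. Power with schools as the unit.** The documents give no ICC, so 0.005, 0.01 and 0.02 are assumptions. With k schools per arm and m = 240 pupils per school:

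variance of the difference = [p1(1−p1) + p2(1−p2)] × [1 + (m−1)·ICC] / (m·k)

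Power is from the noncentral t distribution on 2k−2 degrees of freedom, one-sided 5%. At ICC 0.01 and k = 4, the design effect is 1 + 239 × 0.01 = 3.39. The variance is (0.0764 + 0.1390) × 3.39 / 960, the standard error 0.0276 and the noncentrality 0.0834 / 0.0276 = 3.02. On 6 df, power is 85%.

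| Scenario | Rates per 100 pupils | ICC 0.005 | ICC 0.01 | ICC 0.02 |
|---|---|---|---|---|
| 4 v 4, full year, every flag a true case | 8.34 v 16.68 | 95% | 85% | 66% |
| 4 v 4, 80% of flags relevant in both arms | 10.4 v 20.9 | 98% | 92% | 75% |
| 4 v 4, half-year window | 4.17 v 8.34 | 73% | 57% | 40% |
| 4 v 4, 80% relevant and half-year | 5.21 v 10.4 | 82% | 66% | 47% |
| 2 v 2 (480 per arm taken literally), full year | 8.34 v 16.68 | 54% | 42% | 30% |

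A beta-binomial simulation agreed with every row to within about 1.5 percentage points.

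**6. Where 90% is lost.** For 4 v 4 schools, power falls to 90% at ICC 0.0075 in the first row, 0.011 with 80% relevance and 0.0012 with the half-year window. If children with a disorder could be counted (0.278 × 240 = about 67 per school, 30% v 60%), 4 v 4 schools would hold 90% up to ICC of about 0.058 one-sided or 0.038 two-sided. For 2 v 2 on that denominator, power is 87%, 81% and 70% at the three ICCs.

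**7. Scale of variation.** If schools vary by a constant coefficient of variation (CV) of 0.33, which matches ICC 0.01 in the control arm, the first row gives 69% and not 85%.

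**The case against.** The strongest reply is that this is a pilot of feasibility and preliminary effectiveness, and that the plan does not rely on 56 because it expects far more children. Several parts of this stand.

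- The sidedness slip is conservative on its own, and 201 pupils is well below 480. Even for 8.34 v 16.68 per 100, independent children would need only 268 per arm one-sided or 329 two-sided. The missing school term is what matters.
- With four schools of 240 per arm and a low ICC, power could exceed 90%. The evidence does not show that the trial is underpowered.
- The plan also states the effect per 100 children per year, which the register and enrolment counts could approximate.
- The side scenarios are open to challenge. The half-year window follows the crossover in months 18 to 24 after a month-12 start, but the first-stage text in section 3.1 places the teacher intervention in months 7 to 18 and the Summary speaks of 12 months. The work plan runs the course for both groups (G1 and G2) within months 7 to 18. Equal 80% relevance in both arms is an assumption; hypothesis 3 sets above 80% as a target. Since the text repeatedly gives four schools per arm, 480 may simply be an uncorrected figure.
- A neighbourhood term would leave 5 df, which moves the first row slightly, to 94%, 83% and 64%.

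None of this restores the claim. A pilot need not be powered, but this one states 90% power and plans a significance claim on the same outcome. The larger sample consists of more pupils in the same schools, which leaves the between-school variance as it was.

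**Conclusion.** The concern holds. The figure of 56 does not follow from the stated one-sided 5% test under the standard formula, it refers to children with a disorder and not to pupils, and it treats children as independent in a trial that assigns eight schools. The 480 per arm contradicts four schools per arm.

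The correct conclusion is that 90% power is not established, not that power is low. On the full-year rates with 4 v 4 schools, power is 95%, 85% or 66% at assumed ICCs of 0.005, 0.01 and 0.02. Across all the scenarios tabulated it runs from 30% to 98%. These figures rest on assumed ICCs, 240 pupils in every school and 27.8% prevalence throughout. Section 1.1 gives 16.5% for ages 12 to 18; if two of the eight grades were that age (an assumption), prevalence would be 25.0%, and the first row would become 93%, 81% and 61%.

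**What to change.** Rewrite the sample-size paragraph in section 3.1 and the text that depends on it:

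1. Withdraw the statement of 90% power with 56 children, or label 56 as the two-sided figure for individually randomised children with a disorder. Make the sidedness and the number agree.
2. Correct 9 and 18 per 100 to 8.3 and 16.7.
3. Reconcile the number and location of schools across section 3.1 and the work plan in section 3.3. Section 2.1 also needs checking, since it speaks of eight schools in each neighbourhood. Then restate pupils per arm (960 if four schools per arm).
4. Define the outcome as detections per 100 enrolled pupils over a stated window that ends before control schools receive the intervention.
5. Compare school-level rates with t degrees of freedom suited to eight schools, not pooled children, and include a neighbourhood term if the reconciled design allocates within neighbourhoods.
6. Report power over a stated range of ICC or CV, or drop the power claim and present the result as a pilot estimate with a confidence interval.

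The cost is wording and analysis only, with no extra enrolment. The stated power becomes less favourable, and confidence intervals will be wider than a pooled-child analysis would give.
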